# 4.3. Determination of Sample Size

The planned number of Relapse events for the double-blind R/WD Phase is 49 in children and adolescents. This number of events will provide 85% power to detect a difference between treatment groups, assuming a hazard ratio of 0.4 for Relapse and statistical testing at alpha level 0.05 (2-sided). Subject enrollment will stop around the time that 49 Relapse events among children and adolescents are anticipated to have occurred. The number of Relapse events among adults will not determine study completion.

Assuming the proportion of subjects who Relapse in the DB randomization phase is 65% in the placebo group and 34% in the ecopipam group, approximately 98 subjects (49 subjects per group) will be required to achieve this number of Relapse events.

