# 6.3. Modified Intent-to-Treat (Primary Efficacy Analysis Set)

The Modified Intention-to-Treat (mITT) set will include all randomized subjects who received at least one dose of study drug post randomization. The mITT set will be used for the analysis of primary, secondary and exploratory efficacy endpoints. Subjects will be analyzed according to randomized treatment.

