# 10. Efficacy

# 10.1. Primary Efficacy Endpoint and Analysis

The YGTSS is a clinician-rated, multi-dimensional instrument for assessing tic symptoms in children and adults with TD. It includes a semi-structured interview with either caregivers (for subjects <18 years of age) or adult subjects (≥ 18 years of age) and clinical observations that assess tic and tic-related impairment severity over the previous week. Every attempt should be made, per subject, to complete interview by the same caregiver or subject and same rater for all visits.

Both motor and vocal tics are assessed for symptom number, frequency, intensity, complexity, and interference on a 0–5 Likert scale. Scores from each dimension are totaled to reflect the severity of motor tics (range 0–25), vocal tics (range 0–25) and combined tics, or Total Tic Score (-TSS) (range 0–50). A separate tic-related impairment scale, scored from 0 to 50, is also included and calculated for the Global Severity score (-GS).

YGTSS will be assessed at Screening, Baseline and at Weeks 4, 8, 12, 13, 14, 15, 16, 18, 20, 22, 24 and 7 day follow up visit.

The primary efficacy endpoint is time from Randomization to Relapse defined as a loss of ≥ 50% of the improvement experienced on the YGTSS-TTS from Baseline to the last visit in the open-label Stabilization period (Week 12), or initiation of additional medications to treat symptoms of TD, or requirement of hospitalization for worsening symptoms of TD in subjects ≥ 6 and < 18 years during the double-blind R/WD period for ecopipam compared to placebo. Data from subjects who complete or discontinue from the double-blind R/WD period without Relapse will be considered as censored observations. The log rank test will be the primary test of statistical significance. Kaplan-Meier curves will be used to compare the times to relapse between the treatment groups. The hazard ratio and its 95% confidence interval (CI) will be estimated from the Cox proportional hazard model with treatment as a factor. The proportional hazards assumption will be evaluated graphically and analytically, for example by assessing martingale and Schoenfeld residuals and by modeling time-dependent covariates.

The analysis of the primary efficacy endpoint will be performed in the mITT (primary), ITT, and PP populations according to the randomized treatment.

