# 13. Interim Analysis

An interim analysis (IA) will be conducted after approximately 70% of Relapse events have accrued (34 Relapse events). The interim analysis will be performed by an independent statistician and governed by an independent Data Safety Monitoring Board (DSMB). The DSMB will consist of a physician experienced in the conduct of clinical studies (Chairman with TD experience), one clinician and one statistician experienced in TD will review the data at the interim analysis. The data will be cleaned by the data management group, and the analysis and reporting of the interim data to the DSMB will be the responsibility of an independent statistical group (which will not be directly involved in the conduct of the study). The DSMB will meet after the data presentation and issue recommendations. Minutes of the DSMB will be submitted to the sponsor after the study has been unblinded and will be appended to the final study report.

The 2-sided alpha level for the IA is 0.005. For the final analysis the 2-sided alpha level after IA spend will be 0.0492. If the statistical significance is reached at the IA, the DSMB can recommend stopping the study for overwhelming efficacy. However, the interim decisions for stopping for futility or potential sample size adjustments are based on the conditional power described below.

The primary efficacy endpoint is time from Randomization to Relapse defined as a loss of  $\geq$  50% of the improvement experienced on the YGTSS-TTS at the last visit in the open-label Stabilization period (Week 12), or initiation of additional medications to treat symptoms of TD, or requirement of hospitalization for worsening symptoms of TD in subjects  $\geq$  6 and < 18 years during the double-blind R/WD period for ecopipam compared to placebo. The analysis will be performed on all randomized subjects in R/WD period. The analysis method will be the same as the primary efficacy analysis as described in Section 10.1.

Assume that r is the number of Relapse events at interim analysis (r=34 in the planned interim analysis), R is the planned number of Relapse events (R=49) in this study, then the conditional power (CP) can be expressed as

CP=1-
$$\Phi(z_{int}\sqrt{\frac{r}{R-r}}+Z_{\alpha/2}\sqrt{\frac{R}{R-r}}+Z_{int}\sqrt{\frac{R-r}{r}})$$

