where  $\Phi(.)$  denotes the cumulative distribution function of the standard normal distribution, and  $z_{\alpha/2}$  denotes the  $1-\alpha/2$  quantile of the standard normal distribution, and  $Z_{int}$  is z-value at interim analysis, which can be obtained from the output of PROC LIFETEST in SAS. The  $Z_{int}$  can be derived from the reported Logrank statistics and the corresponding covariance matrix

Derivation:

$$Z_{int} = \frac{O - E}{\sqrt{V}} = \frac{\sum_{j} (O_j - E_j)}{\sqrt{\sum_{j} V_j}}$$

where,

 $O_i = d_{1i}$ , Number of subjects in Ecopipam who developed Relapse, at distinct time j

This document is confidential.

SAP text Version: SAP text 3.0 6-Dec-2023

Controlled Document ID: 3903A.02, Effective Date 31-Aug-2020

$$E_j = \left(\frac{Y_{1j}}{Y_j}\right) * d_j, \qquad d_j = d_{0j} + d_{1j}, \text{ total number of Relapses at time j, } Y_{1j} = \text{Number of subjects in Ecopipam at time } j,$$

 $Y_i$  = Number of subjects at risk at time j.

$$V_j = \frac{Y_{0j}Y_{1j}d_j(Y_j-d_j)}{Y_i^2(Y_j-1)}, Y_{0j} = \text{number of subjects at risk at time j at control arm,}$$

 $d_i = d_{0j} + d_{1j}$  total number of Relapses at both control arm and Ecopipam at time j.

Based on the results of the above conditional power and the promising zone approach [8], the DSMB may make the following interim decisions:

- If p-value based on Logrank test at interim analysis is less than 0.005 and other measures (e.g., hazard ratio) imply a benefit of ecopipam over placebo, it is recommended to stop the study for overwhelming efficacy.
- 2) If 50%<CP<85%, then increase the number of required events such that CP based on the adjusted events ≥85% or reach the maximum number of Relapse events allowed, defined as two times the planned Relapse events (49 x 2 = 98).
- 3) If condition power (CP)<20%, it is recommended to stop the study for futility.
- 4) If all other cases, continue this study as planned.

No adjustment of the final alpha level will be required, other than the alpha spending of the IA, based on the CP approach.

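### SAP 13 words the interim population as all randomized subjects, with no age limit, although its endpoint, reference analysis and event target concern ages 6 to under 18

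*SAP*

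**What the plan says.** SAP 13 describes the interim test in three consecutive sentences. The first restates the primary endpoint, time to Relapse at ages 6 to under 18. The second is "The analysis will be performed on all randomized subjects in R/WD period". The third is "The analysis method will be the same as the primary efficacy analysis as described in Section 10.1".

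Other parts of the SAP bear on the second sentence:

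- **Analysis sets.** Section 10.1 states "The analysis of the primary efficacy endpoint will be performed in the mITT (primary), ITT, and PP populations according to the randomized treatment". Section 6.3 states "The Modified Intention-to-Treat (mITT) set will include all randomized subjects who received at least one dose of study drug post randomization". Section 6.4 defines the ITT set simply as every randomized subject. None of these sets has an age limit.
- **Event target.** Section 4.3 states "The planned number of Relapse events for the double-blind R/WD Phase is 49 in children and adolescents" and adds "The number of Relapse events among adults will not determine study completion".
- **Interim quantities.** Section 13 sets r = 34 and R = 49, caps any increase at 98 events, and defines the ecopipam log-rank count as "Number of subjects in Ecopipam who developed Relapse, at distinct time j". Neither r nor the log-rank terms name an age group.
- **Protocol 13.3.** It gives 34 events without an age range or analysis set and leaves full details to the SAP.

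**The concern.** The second sentence states a population, and it differs from its neighbours in two ways. It drops the age range of the endpoint, and it uses the ITT wording where Section 10.1 makes mITT primary.

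The SAP does not settle the age range by usage elsewhere. Sections 10.2.21 and 10.2.22 use almost the same phrase for endpoints with no age limit. Section 10.2.1 applies the Section 10.1 method irrespective of age, so a reference to that method does not by itself carry the age range.

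One statistic, Z_int, drives the stop for efficacy, the stop for futility and the increase in events. An independent statistical group computes it. If that group follows the sentence to the letter, adult relapses enter Z_int while R = 49 is a pediatric count. Adult relapses could then help to end the study, contrary to Section 4.3, and the interim decision would no longer describe the final primary test.

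**Working it through.** **Inputs from the documents.** SAP 4.3: 49 events, 85% power, hazard ratio 0.4, two-sided 0.05, relapse 65% on placebo and 34% on ecopipam, 49 children and adolescents per group, 50% response, about 40 adults enrolled. SAP 13: 34 interim events, two-sided levels 0.005 and 0.0492, futility below 20% conditional power.

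**Assumptions, not in the documents.** 20 adults randomized (40 × 0.50; range 10 to 30). Adult and pediatric events accrue in proportion. Either adults have the pediatric effect with 49.5% relapse, the mean of 65% and 34%, or they have hazard ratio 1 with 65% relapse in both arms. Conditional power uses 0.0492.

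**1. The plan's own figures.** Freedman's formula gives ((1+0.4)/(1−0.4))² × (1.960+1.036)² = 5.444 × 8.978 = 48.9, so 49 events. Expected events are 49×0.65 + 49×0.34 = 48.5. The information fraction is 34/49 = 0.694. At that fraction the pair 0.005 and 0.0492 gives an overall two-sided alpha of 0.04995. All of this fits a pediatric interim.

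**2. Pediatric interim as benchmark.** Let Z = −Z_int, so that positive values favour ecopipam. At 85% power the mean of Z is 2.996 at 49 events and 2.996 × √(34/49) = 2.496 at 34.

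- Efficacy stop: 1 − Φ(2.807 − 2.496) = 37.8%.
- Conditional power: Φ(Z√(34/15) − 1.967√(49/15) + Z√(15/34)), which equals 20% at Z = 1.25. Futility stop: Φ(1.25 − 2.496) = 10.6%.

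**3. Literal reading, 34 events pooled over all ages.** Let a be the adult events expected beside 48.5 pediatric ones. The pediatric share is s = 48.5/(48.5 + a). With an equal adult effect the mean of the pooled Z stays at 2.496. With adult hazard ratio 1 it is s × 2.496. For 20 adults, a is 9.9 (equal effect, s = 0.831) or 13 (hazard ratio 1, s = 0.789).

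| Adults randomized | Adult effect | Pediatric events among 34 | Mean of Z | Efficacy stop | Futility stop |
|---|---|---|---|---|---|
| none in test | – | 34 | 2.496 | 37.8% | 10.6% |
| 10 | equal | 30.9 | 2.496 | 37.8% | 10.6% |
| 20 | equal | 28.2 | 2.496 | 37.8% | 10.6% |
| 30 | equal | 26.0 | 2.496 | 37.8% | 10.6% |
| 10 | HR 1 | 30.0 | 2.201 | 27.2% | 17.1% |
| 20 | HR 1 | 26.8 | 1.968 | 20.1% | 23.6% |
| 30 | HR 1 | 24.3 | 1.780 | 15.2% | 29.8% |

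**4. Whose data carry an efficacy stop.** With 20 adults and an equal effect, the pediatric Z at the same look has mean 2.996 × √(28.2/49) = 2.273 and correlation √0.831 = 0.911 with the pooled Z. The bivariate normal probability that the pooled Z exceeds 2.807 and the pediatric Z does not is 11.0% (7.1% with 10 adults, 14.1% with 30).

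**5. Type I error.** With no effect at any age, and leaving the event increase aside, the pooled interim Z and the final pediatric Z have correlation s × √(34/49). For 20 adults this is 0.692 or 0.657, and overall alpha is 0.0512 or 0.0515. Over 10 to 30 adults it runs from 0.0507 to 0.0520, against 0.04995.

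**The case against.** The best defence is that the sentence follows the SAP's own convention. No analysis set has an age limit, and the endpoint supplies it. Section 10.1 is built the same way, and nobody would say that the final primary analysis includes adults. Section 10.1 also restates the age range, so the cross-reference in SAP 13 leads back to it. R = 49, the cap of 98 and the statement that adult relapses do not determine completion all point in the same direction. The stop rules are recommendations that the DSMB may make, and the charter, which is not among the documents, may already name the population.

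Most of this stands. It makes the pediatric reading the likely one and the point minor. It does not remove the conflict, because the sentence states a population, and the same phrase covers all ages in Sections 10.2.21 and 10.2.22.

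A reader might infer that the plan will pool adults at the interim, or that 49, 34 or 0.0492 is wrong. The documents support neither inference. The figures reproduce, and they fit a pediatric interim.

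A reader might also infer that adults would raise the chance of an early efficacy stop. With an equal adult effect that rate rises to 47.3% only if the look is triggered at 34 pediatric events and about 7 adult events are then added to the test. That applies the age limit to the trigger and drops it for the test, and the gain comes from testing about 41 events rather than 34.

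**Conclusion.** The point holds as a minor one about the wording of a decision rule. SAP 13 gives an interim population that does not agree with its own endpoint, with the primary set of Section 10.1, or with the pediatric event target.

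The consequence depends on adult response and relapse rates, which the documents do not give. If adults respond like children, pooling leaves the stop rates where they were, but about one trial in nine would stop for efficacy without the pediatric data reaching the bound alone. If ecopipam does nothing in adults, pooling costs efficacy stops (about 38% to 20%) and adds futility stops (about 11% to 24%). Hazard ratio 1 in adults is an illustration that nothing in the documents supports. Type I error is not a material concern.

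The ITT versus mITT difference should matter little. Drug is dispensed at the Week 12 randomization visit, so few subjects should be randomized and not dosed, and Section 10.1 runs the ITT analysis as well.

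**What to change.** Before anyone sees unblinded interim data, replace the sentence in SAP 13 with:

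*The interim log-rank test, Z_int, r (including the 34 trigger events) and R use subjects ≥6 and <18 years in the mITT set, as in the final primary analysis (ITT supportive).*

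Then check that the DSMB charter names the same population. Timing matters, because a choice of population made after the interim data are known could look data-driven.

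The cost is one SAP sentence and a charter check. No number changes, and no patients or analyses are added. No protocol amendment is needed, because 34 is already about 70% of the pediatric 49.

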# 14. Changes from Analysis Planned in Protocol

There are no changes from the analysis planned in protocol.

# 16. Appendices

# 16.1. Schedule of Assessments

		Open-Label Stabilization Period															
	Screening Period a								Safety Follow-Up (Days 170-199)								
Visit/TC Study Day	Screening VISIT 1 Day -28 to -1	Baseline VISIT 2 Day 1	W 2 f Day 15 Telephone call only (±3d)	W4 / VISIT 3/ Day 29 (±3d)	W8 / VISIT 4 / Day 57 (±3d)	W 12 VISIT 5 Day 85 (±3d)	W13 / VISIT 6 / Day 92 (±3d)	W14 / VISIT 7 / Day 99 (±3d)	W15 / VISIT 8 / Day 106 (±3d)	W16 / VISIT 9 / Day 113 (±3d)	W18 / VISIT 10 / Day 127 (±3d)	W20 / VISIT 11 / Day 141 (±3d)	W22 / VISIT 12/ Day 155 (±3d)	W 24 VISIT 13 Day 169 or Relapse or ET (±3d)	7 Day F/U VISIT 14 (±3d)	14 Day F/U VISIT 15 (±3d)	30 Day F/U f Telephone call only (±3d)
Informed Consenta	X																
DSM-5-TR Criteria for TD	X																
Inclusion/ Exclusion	X	X															
Medical/Psychiatric / Medication History	X	X															
Randomization						X											
Physical Exam/Vital Signs b	X	X		X	X	X	X	X	X	X	X	X	X	X	X	X	
ECG b	X	X		X		X					X			X	X	X	
Central Laboratory tests (Hematology, Chemistry, Urinalysis, HbA1c, Prolactin) c	X	Х				X					X			X	Х	X	

This document is confidential.

SAP text Version: SAP text 3.0 6-Dec-2023

Controlled Document ID: **3903A.02**, Effective Date 31-Aug-2020

		Open-Label Stabilization Period															
	Screening Period a	Titrati	Maintenance Phase Weeks 4 to 12 Weeks 4 to 12 Weeks 12 to 24 (Day 29 up to 84)  Maintenance Phase Weeks 12 to 24 (Days 85 to 169)							Safety Follow-Up (Days 170-199)							
Visit/TC Study Day	Screening VISIT 1 Day -28 to -1	Baseline VISIT 2 Day 1	W 2 f Day 15 Telephone call only (±3d)	W4 / VISIT 3/ Day 29 (±3d)	W8 / VISIT 4 / Day 57 (±3d)	W 12 VISIT 5 Day 85 (±3d)	W13 / VISIT 6 / Day 92 (±3d)	W14 / VISIT 7 / Day 99 (±3d)	W15 / VISIT 8 / Day 106 (±3d)	W16 / VISIT 9 / Day 113 (±3d)	W18 / VISIT 10 / Day 127 (±3d)	W20 / VISIT 11 / Day 141 (±3d)	W22 / VISIT 12/ Day 155 (±3d)	W 24 VISIT 13 Day 169 or Relapse or ET (±3d)	7 Day F/U VISIT 14 (±3d)	14 Day F/U VISIT 15 (±3d)	30 Day F/U f Telephone call only (±3d)
Central Urine Drug Screen	X	X		X	X	X	X	X	X	X	X	X	X	X	X	X	
Local Urine Pregnancy Test i	X	X		X	X	X	X	X	X	X	X	X	X	X	X	X	
Yale Global Tic Severity Scale	X	X		X	X	X	Х	X	X	X	X	X	X	X	X		
Clinical Global Impression – Tourette Syndrome Severity	X	X		X	X	X	X	X	X	X	X	X	X	X			
Clinical Global Impression – Tourette Syndrome Improvement				X		X	X	X	X	X	X	X	X	X			
Caregiver Global Impression of Change h				X		X					X			X			
Gilles de la Tourette Syndrome – Quality of Life Scale for Children and Adolescentsh		X				X								X			
Gilles de la Tourette Syndrome – Quality of Life Scale g		X				X								X			

This document is confidential.

SAP text Version: SAP text 3.0 6-Dec-2023 Controlled Document ID: **3903A.02**, Effective Date 31-Aug-2020 Filing requirements: TMF

		Open-Label Stabilization Period															
	Screening Period a								Safety Follow-Up (Days 170-199)								
Visit/TC Study Day	Screening VISIT 1 Day -28 to -1	Baseline VISIT 2 Day 1	W 2 f Day 15 Telephone call only (±3d)	W4 / VISIT 3/ Day 29 (±3d)	W8 / VISIT 4 / Day 57 (±3d)	W 12 VISIT 5 Day 85 (±3d)	W13 / VISIT 6 / Day 92 (±3d)	W14 / VISIT 7 / Day 99 (±3d)	W15 / VISIT 8 / Day 106 (±3d)	W16 / VISIT 9 / Day 113 (±3d)	W18 / VISIT 10 / Day 127 (±3d)	W20 / VISIT 11 / Day 141 (±3d)	W22 / VISIT 12/ Day 155 (±3d)	W 24 VISIT 13 Day 169 or Relapse or ET (±3d)	7 Day F/U VISIT 14 (±3d)	14 Day F/U VISIT 15 (±3d)	30 Day F/U f Telephone call only (±3d)
Premonitory Urge for Tics Scale		X		X		X					X			X			
Columbia Suicide Severity Rating Scale	X	X	X	X	X	X	X	X	X	X	X	X	X	X	X	X	
Children's Depression Rating Scale – Revised h	X	X		X	X	X	X	X	X	X		X		X			
Pediatric Anxiety Rating Scale h		X		X	X	X	X	X	X	X		X		X			
Extrapyramidal Symptom Rating Scale		X		X	X	X	X	X	Х	X	X	X	X	X			
Swanson, Nolan, and Pelham Questionnaire-IV- 26 h		Х		X	Х	X	X	X	X	X		X		X			
Children's Yale- Brown Obsessive Compulsive Scale- II h		X		Х	X	X	X	X	Х	X		X		Х			
Patient Health Questionnaire-9g	X	X		X	X	X	X	X	X	X		X		X			

This document is confidential.

SAP text Version: SAP text 3.0 6-Dec-2023 Controlled Document ID: **3903A.02**, Effective Date 31-Aug-2020 Filing requirements: TMF

			Open-Label	Stabilizatio	on Period												
	Screening Period a			W	faintenance Phase Weeks 4 to 12 Day 29 up to 84)		Double-Blind Randomized Withdrawal Period Weeks 12 to 24 (Days 85 to 169)								Safety Follow-Up (Days 170-199)		
Visit/TC Study Day	Screening VISIT 1 Day -28 to -1	Baseline VISIT 2 Day 1	W 2 f Day 15 Telephone call only (±3d)	W4 / VISIT 3/ Day 29 (±3d)	W8 / VISIT 4 / Day 57 (±3d)	W 12 VISIT 5 Day 85 (±3d)	W13 / VISIT 6 / Day 92 (±3d)	W14 / VISIT 7 / Day 99 (±3d)	W15 / VISIT 8 / Day 106 (±3d)	W16 / VISIT 9 / Day 113 (±3d)	W18 / VISIT 10 / Day 127 (±3d)	W20 / VISIT 11 / Day 141 (±3d)	W22 / VISIT 12/ Day 155 (±3d)	W 24 VISIT 13 Day 169 or Relapse or ET (±3d)	7 Day F/U VISIT 14 (±3d)	14 Day F/U VISIT 15 (±3d)	30 Day F/U f Telephone call only (±3d)
Hamilton Rating Scale for Anxiety g		X		X	X	X	X	X	X	X		X		X			
Conners' Adult ADHD Rating Scale g		X		X	X	X	X	X	Х	Х		X		X			
Yale-Brown Obsessive Compulsive Scale- II g		X		X	X	X	X	X	X	X		X		X			
PK Blood Draws d,e				X	X	X											
Adverse Events	X	X	X	X	X	X	X	X	X	X	X	X	X	X	X	X	X
Concomitant Medications	X	X		X	X	X	X	X	X	X	X	X	X	X	X	X	
Dispense Study Drug		X		X d	X	X				X		X		X			
Collect Unused Study Drug/Assess Drug Compliance		1.61		X	X	X	X	X	X	X	X	X	X	X	X		

Abbreviations: ADHD = attention-deficit hyperactivity disorder; AE = adverse event; BP = blood pressure; DSM-5-TR = Diagnostic and Statistical Manual of Mental Disorders, Fifth Edition; ECG = electrocardiogram; F/U = follow up; HR = heart rate; PK = pharmacokinetic(s); TD = Tourette's Disorder

This document is confidential.

SAP text Version: SAP text 3.0 6-Dec-2023

Controlled Document ID: 3903A.02, Effective Date 31-Aug-2020

<sup>a Informed consent must be obtained prior to any screening procedures. All screening procedures are to occur after confirmation of appropriate timeframe since discontinuation of applicable medications. Rescreening is allowed after approval by the Medical Advisor.

#### Statistical Analysis Plan for Interventional Studies

Sponsor: Emalex Biosciences, Inc.; Protocol No.: EBS-101-TD-301

- b Vital signs will include, pulse, BP (done 5 minutes after being supine and prior to the ECG), height and weight.
- c Subjects should be in a fasting state (8 hours) for laboratory tests. Fasting at the Screening visit is optional. HbA1c will be measured only at Baseline, Week 12, and Week 24 (completed subjects only).
- d. At Week 4, ecopipam should be administered after the pre-dose blood draw. PK samples will be collected at 1) pre-dose; 2), post-dose between 0.5 and 1.5 hours; and 3) post-dose between 2 and 4 hours. Week 12 PK assessment only to be performed if Week 8 assessment is missed.
- e If visits at Weeks 4, 8 and/or 12 are completed in locations other than study clinic due to restrictions because of the COVID-19 pandemic or other qualifying event, then collection of labs for PK assessments are optional.
- Week 2 and 30-Day FU visits will be a telephone call. If there are any abnormal findings, the subject will be brought to the site for full assessment. Subjects who complete the Baseline visit for the EBS-101-TD-391 open label extension study within 30 days of the Week 24 visit are not required to complete the 30-Day FU telephone call.
- g Administration applicable to adult subjects only.
- h Administration applicable to child and adolescent subjects only (6-17 years of age).
- 1 For women of childbearing potential only. If positive, request a serum HCG on the Chemistry blood sample requisition form for confirmation of pregnancy.

This document is confidential.

SAP text Version: SAP text 3.0 6-Dec-2023

Controlled Document ID: 3903A.02, Effective Date 31-Aug-2020

